#### **11.4 Interim Analysis and Early Stopping Guidelines**

An interim analysis is planned after enrollment in Stage 1 is complete and the primary efficacy endpoint is determined for all response-evaluable patients who are enrolled in stage 1 based on the first 6 cycles of protocol therapy. A patient is considered response-evaluable if they meet the criteria described for the per-protocol population in Section 11.5. Based on the continuation criterion described in Section 11.3, enrollment will either continue into stage 2 or will be limited to patients whose tumors display the correct master regulator profile consistent with sensitivity to entinostat.

Safety will be assessed in an ongoing fashion based on the incidence of adverse events, serious adverse events, and treatment discontinuations due to adverse event. No formal safety stopping rules are specified. However, if any significant safety issues arise, a decision to modify or terminate the trial will be made.

## 11.5 Planned Methods of Analysis

The full analysis set (FAS) population will include all patients who are enrolled in the study. A patient is considered enrolled in the study once the patient or legal representative grants written informed consent. The FAS population will serve as the population for a supportive analysis of the primary efficacy analysis.

The per-protocol population (evaluable patients) will serve as the population for the primary analysis of the efficacy data in this study. The per-protocol population is a subset of the FSA population and will include patients who meet all of the following criteria:

- Complete at least **two** cycles of entinostat therapy, irrespective of dose level.
- Undergo CT scans at Screening and day 1 of cycle 3.

The safety population consists of all patients who receive at least one dose of study drug. At least one laboratory or vital sign measurement obtained subsequent to at least one dose of study drug is required for inclusion in the analysis of each safety specific parameter. To assess change from baseline, a baseline measurement is also required.

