## **1. OBJECTIVES**

### **1.1 Primary**

The primary objective of this study is to estimate the objective response rate with entinostat in patients with relapsed or refractory abdominal neuroendocrine tumors. Objective response will include complete response (CR) and partial response (PR) and will be determined from each patient's best response that is documented during protocol therapy.

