### **11.3 Sample Size Considerations**

#### **11.3.1 Initial Protocol**

Up to 40 patients may be enrolled to achieve 32 response-evaluable patients. It's anticipated that no more than 25% of enrolled patients will be non-evaluable for response.

The sample size for the expansion phase is based on a Simon 2-stage design (optimum version) and objective response rate endpoint described in Section 11.2. To calculate the required sample size, the following assumptions were made. The response probability of an ineffective therapy in this indication (i.e., the uninteresting response level) was chosen to be 15%; the response probability of an effective therapy (i.e., the targeted response level) was chosen to be at least 35%, level of significance of 10%, and power of 80%. Based on these

assumptions, the sample size of the first and second stage is 9 and 14, respectively, for a total of 23 response-evaluable patients (see below).

- If less than 2 of the 9 patients achieve an objective response (CR or PR) during the first stage of the study, enrollment will be terminated for unselected patients and entinostat will be declared to have insufficient activity in this indication in unselected patients. Thereafter, enrollment will be restricted to patients whose tumors display the characteristic master regulator expression profile consistent with hypothesized entinostat sensitivity.
- If 6 or more unselected patients achieve objective response after completion of the second stage, then entinostat will be considered sufficiently promising in this treatment setting and may be evaluated in future studies.
- If the total number of patients with objective response after completion of the second stage is between 2 and 5, further development of entinostat in this indication will be assessed. If the true objective response rate for entinostat is  $\leq 15\%$ , then the expected sample size is 14.61 patients, with probability of terminating the study at the end of the first stage equal to 60%.

Up to 40 patients may be enrolled to achieve 32 response-evaluable patients (9 unselected patients in stage 1, and 23 selected patients in stage 1 and 2).

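### The only success count names unselected patients, so after a failed stage 1 no decision rule applies to the selected cohort, and the primary population is not split by cohort

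*Combined protocol and SAP*

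**What the plan says.** Section 11.3.1 sets up a Simon optimal two-stage design in which "the sample size of the first and second stage is 9 and 14, respectively, for a total of 23 response-evaluable patients". The synopsis repeats the text.

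- **Stage 1.** With fewer than 2 responders among 9, unselected enrollment ends and later patients must show the master regulator profile.
- **Success.** The drug is called sufficiently promising under a condition that begins "If 6 or more unselected patients achieve objective response after completion of the second stage".
- **Middle zone.** A total of 2 to 5 responders leads to further assessment. This bullet does not name a cohort.
- **Accrual.** The 32 evaluable patients are broken down as "9 unselected patients in stage 1, and 23 selected patients in stage 1 and 2".

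Section 11.4 describes one interim analysis, the one that decides whether unselected enrollment goes on into stage 2 or is limited to selected patients.

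Section 11.5 states: "The per-protocol population (evaluable patients) will serve as the population for the primary analysis of the efficacy data in this study". Membership needs two completed cycles and CT scans at screening and at day 1 of cycle 3. Neither criterion refers to the profile. The primary objective in section 1.1 is likewise undivided: to "estimate the objective response rate with entinostat in patients with relapsed or refractory abdominal neuroendocrine tumors".

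Inclusion criterion 2 (section 4.1 and synopsis) makes eligibility for stage 2 depend on the RNAseq profile.

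**The concern.** The success rule and the enrollment rule do not fit together. Once stage 1 fails, at most one unselected patient has responded and no more will be enrolled, so the success count cannot be met whatever happens in the selected cohort. The three bullets of section 11.3.1 then leave a gap: 6 or more responders among selected patients falls under none of them, because the unselected count is at most 1 and the total is not between 2 and 5.

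Selected patients are the group that the first scientific hypothesis in section 2.5 concerns. As the text stands, up to 23 of them could be treated with no written interim look, no threshold and no stated separate estimate. The denominator and the threshold would then be chosen after the responses are known.

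**Working it through.** **Inputs.** From section 11.3.1: null rate, "the uninteresting response level) was chosen to be 15" percent; then "the targeted response level) was chosen to be at least 35%, level of significance of 10%, and power of 80" percent; stage sizes 9 and 14; stage 1 fails at 0 or 1 responder; success at 6 or more of 23. No response rate is given for selected patients, so 35% (the design target) is an assumption, varied below from 25% to 50%.

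**1. Reproduce the plan's figures.**
- Probability of failing stage 1: P(X ≤ 1) = (1−p)^9 + 9p(1−p)^8. At p = 0.15 this is 0.2316 + 0.3679 = 0.5995, the stated 60%.
- Expected sample size at 0.15: 9 + 14 × (1 − 0.5995) = 14.61, as stated.
- Probability of a positive call: the sum over x = 2 to 9 of P(Bin(9,p) = x) × P(Bin(14,p) ≥ 6 − x). This is 0.0990 at p = 0.15 and 0.8037 at p = 0.35, within the stated 10% and 80%.
- An exact search over designs of up to 40 patients returns the same 9/23 design as optimal.

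The design itself is sound. The issue is which patients its counts apply to.

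**2. How likely is the branch?** 60% at an unselected rate of 15%. At an assumed 10% it is 0.9^9 + 9 × 0.1 × 0.9^8 = 0.387 + 0.387 = 0.775. At 35% it is 12%.

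**3. Can the success count be met on this branch?** Unselected responders ≤ 1, further unselected enrollment = 0, required = 6. It cannot.

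**4. What if section 11.5 is applied as one set of 32?** With k stage 1 responders (0 or 1) and selected rate s, the expected pooled rate is (23s + k)/32 and the loss is s minus that.

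| s (assumed) | k = 0: pooled rate, loss | k = 1: pooled rate, loss |
|---|---|---|
| 25% | 18.0%, 7.0 points | 21.1%, 3.9 points |
| 35% | 25.2%, 9.8 points | 28.3%, 6.7 points |
| 50% | 35.9%, 14.1 points | 39.1%, 10.9 points |

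For s = 35%, averaging over k given failure: the mean of k is P(1)/(P(0) + P(1)) = 0.3679/0.5995 = 0.61 at an unselected rate of 15%. The pooled rate is then (8.05 + 0.61)/32 = 27.1%, a loss of 7.9 points. At unselected rates of 10% and 5% the losses are 8.3 and 8.8 points.

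**5. What if each cohort has its own 9 + 14 rule?** Each keeps a false positive rate of 0.099 and power of 0.804. The selected cohort opens only if unselected stage 1 fails, so the two ways of making a false call exclude each other. With both cohorts at 15%: 0.0990 + 0.5995 × 0.0990 = 0.158.

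**6. Two uses of stage 2.** Inclusion criterion 2 ties stage 2 eligibility to the profile. The success bullet in section 11.3.1 counts unselected patients at the end of the second stage, and section 11.4 lets unselected enrollment continue into stage 2. Both cannot hold for the same stage.

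**The case against.** The best defense is that the intention is clear enough. Section 11.3.1 ties the sample size to the expansion phase and lists selected patients in both stages, which points to a separate 9 + 14 design for them. Its decision counts rest on 9 and 23. The figure 32 appears only as an accrual total, broken down by cohort. Section 11.4 uses the per-protocol criteria to decide which stage 1 patients are evaluable, so section 11.5 can be read as a patient-level filter. On this view the word unselected in the success bullet is a slip.

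Much of that stands, and it rules out three stronger readings that a reader might infer:

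- *Section 11.5 requires a pooled rate on 32 patients.* It does not. It gives no denominator and does not mention pooling; it is silent on cohorts.
- *The plan bars a positive conclusion for selected patients.* It does not. The bullet gives a sufficient condition for unselected patients. What is missing is a rule for the others.
- *The bias is a fixed 8 points.* That figure needs pooling, an assumed 35% and full accrual of 23. With its own 2-of-9 look, the selected cohort would stop at 9 patients with probability 12% even at 35%, so the total would not always be 32.

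What the defense cannot supply is the rule itself. A bracketed accrual breakdown is not a decision criterion, and the cohort-neutral middle bullet covers only an undecided result.

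**Conclusion.** Wrong as written. On a branch to which the plan itself gives a 60% chance at the null rate, the only success rule cannot be met, no interim look is specified for the selected cohort, and neither section 11.5 nor the primary objective says whether response is estimated by cohort. This conclusion needs no assumption beyond the text.

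The size of any dilution is conditional. It arises only if the silence in section 11.5 is taken as one analysis set. Then, with 9 + 23 evaluable patients and a selected rate of 35%, the loss is 6.7 to 9.8 points; over 25% to 50% it is 3.9 to 14.1 points. The stated sample sizes and error rates are correct.

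**What to change.** - **Section 11.3.1, section 11.4 and the synopsis.** State that the selected cohort is its own 9 + 14 Simon design, with the 2-of-9 and 6-of-23 counts applied to selected patients and an interim look after its first 9. In the 6-of-23 bullet, replace the reference to unselected patients with *patients in the cohort under test*. Say whether the 2-to-5 bullet also counts within a cohort.
- **Section 11.5.** State that the primary response rate is estimated separately for the unselected and selected cohorts, and that any rate on all 32 patients is descriptive only.
- **Inclusion criterion 2.** Reconcile it (section 4.1 and synopsis) with sections 11.3.1 and 11.4 on who may enter stage 2.
- **Error rates.** Report the chance of about 15.8% of at least one false positive call when both cohorts are at 15%, beside the 9.9% per cohort.

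The cost is a few sentences and no additional patients. Two limits remain: the higher overall false positive chance, and an unselected estimate that rests on only 9 patients after a failed stage 1.

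### The primary ORR and both Simon counts leave out treated patients who fail before the cycle 3 scan, so ORR is biased upward; if 15% is the all-treated null rate, the false-positive rate is about 12% to 21%, and at most 26%, against 9.9% by design

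*Combined protocol and SAP*

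**What the plan says.** Section 11.5 sets the primary efficacy population: "The per-protocol population (evaluable patients) will serve as the population for the primary analysis of the efficacy data in this study". Membership has two conditions: finishing two cycles of entinostat at any dose, and imaging, worded as "Undergo CT scans at Screening and day 1 of cycle 3". Section 11.4 carries the definition into the interim decision: "A patient is considered response-evaluable if they meet the criteria described for the per-protocol population in Section 11.5". The 9 and 23 patients in section 11.3.1 are response-evaluable patients, so both decision rules (at least 2 of 9, at least 6 of 23) are counted in this set.

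On losses, section 11.3.1 expects that "no more than 25% of enrolled patients will be non-evaluable for response", and allows 40 enrolled patients to reach 32 evaluable ones. Enrolment is dated from consent: "A patient is considered enrolled in the study once the patient or legal representative grants written informed consent". The FAS is everyone enrolled in that sense, and its analysis is supportive only. A safety population of patients with at least one dose is also defined, but it has no role in efficacy.

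The design rates are "The response probability of an ineffective therapy in this indication (i.e., the uninteresting response level) was chosen to be 15" percent and "the response probability of an effective therapy (i.e., the targeted response level) was chosen to be at least 35" percent, with "level of significance of 10%, and power of 80" percent.

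No section says that progression, death or withdrawal for toxicity before the cycle 3 scan counts as non-response.

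**The concern.** The objective in section 1.1 is the ORR in patients with relapsed or refractory abdominal NET, and section 11.2 bases it on best response while on study drug. Neither is limited to patients who reach week 8.

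Early failures can leave the analysis set. Section 6.2 takes patients off treatment as soon as progression or unacceptable toxicity is documented. Tables 6-1 and 6-2 end treatment after four consecutive held weeks. Both can happen within the first two cycles. Section 7.4 asks for an end-of-treatment CT if progression has not yet been seen, so a patient who stops in cycle 2 may have progression on film and still be excluded. That outcome is known, not missing. Because the plan enrols until the evaluable count is reached, such patients are in effect replaced.

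Two decisions depend on this count: whether unselected enrolment continues after stage 1, and whether entinostat is called sufficiently promising at the end. Both become easier to pass if non-responders are removed. The FAS is no corrective, because it can add patients who never took the drug and so tends to understate the ORR. Neither set gives the ORR in treated patients.

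**Working it through.** **Inputs (section 11.3.1).** Null rate 0.15, target 0.35, level 10%, power 80%. Stage 1 has 9 patients; continue with 2 or more responders. The total is 23 (14 more); success is 6 or more. Stated expected sample size is 14.61 and stated early-stopping probability 60%.

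**Formulas.** With X1 ~ Bin(9, p) and X2 ~ Bin(14, p):

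- PET = P(X1 ≤ 1)
- P(success) = Σ over x = 2 to 9 of P(X1 = x) × P(X2 ≥ 6 − x)
- Expected N = 9 + 14 × (1 − PET)

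**Step 1: reproduce the plan.** At p = 0.15, PET = 0.85^9 + 9 × 0.15 × 0.85^8 = 0.2316 + 0.3679 = 0.5995. Expected N = 9 + 14 × 0.4005 = 14.61. P(success) is 0.0990 at p = 0.15 and 0.8037 at p = 0.35. The plan's figures are reproduced, and a search over designs confirms 9 + 14 as the optimal one.

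**Step 2: remove early failures.** Assume that a share d of treated patients is dropped, that none of them would have responded, and that the true ORR in all treated patients is 15%. The rate among evaluable patients is then 0.15/(1 − d). The same rule at that rate gives:

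| Treated loss d | Evaluable rate | Pass stage 1 | P(success), inactive drug |
|---|---|---|---|
| 0 | 15.0% | 40.1% | 9.9% |
| 5% | 15.8% | 42.8% | 12.0% |
| 10% | 16.7% | 45.7% | 14.5% |
| 15% | 17.6% | 49.0% | 17.6% |
| 20% | 18.75% | 52.5% | 21.4% |
| 25% | 20.0% | 56.4% | 26.0% |

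Each figure is for one run of the two-stage rule in one cohort.

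**Step 3: where the larger losses come from.** (40 − 32)/40 = 20%, which is treated loss only if every loss happens after dosing. The 25% is the plan's stated ceiling. At 25%, 23 evaluable patients come from 23/0.75 ≈ 31 treated, so 6/23 = 26.1% among evaluable patients is 6/31 = 19.4% among treated patients.

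**Step 4: count every treated patient.** If the 9 and 23 are treated patients and early failures count as non-responders, the error is 9.9%, and power is 80.4% if 35% is the all-treated rate. If 35% was meant for evaluable patients, the treated-scale rate is 0.35 × 0.80 = 0.28 at 20% loss (power 58.5%) and 0.35 × 0.75 = 0.2625 at 25% loss (power 51.6%).

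**The case against.** Several points on the other side are sound.

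- **The 25% is not a treated share.** It is a share of patients enrolled at consent. Screen failures and withdrawals before dosing may make up part of it, and excluding them causes no upward bias.
- **Early treated loss may be modest.** Eligibility requires ECOG 0 or 1, section 2.2 describes the drug as well tolerated, and the dose tables allow holds and reductions before discontinuation. The first scheduled on-treatment CT is the cycle 3 scan itself, so progression first seen there stays in the denominator. The documents give no rate for earlier loss.
- **The scale of the 15% is open.** Section 11.3.1 gives 15% and 35% in the same paragraph as a sample size in evaluable patients. If both rates are on the evaluable scale, the error is 9.9% and power 80.4%.
- **Some dropped patients may respond.** A later responder who missed the cycle 3 scan is also excluded, which offsets part of the bias.
- **The consequences are limited.** The objective is to estimate the ORR, reaching 6 of 23 only permits further study, and failing stage 1 moves enrolment to selected patients.

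The first four limit the size of the error inflation and make it conditional. None of them gives early failures a place in the primary analysis. The fifth lowers the stakes, but an estimate of ORR is where the choice of denominator matters most.

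A reader might infer that the trial's true type I error is 26%, or that it certainly exceeds 10%. The documents support neither. The first needs the full 25% to be treated non-responders; both need 15% to be the all-treated rate, which section 11.3.1 does not settle. A reader might also infer that the FAS scores never-treated patients as non-responders. Section 11.5 gives no scoring rule for them; it only admits them.

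**Conclusion.** The concern holds in conditional form. As written, the primary ORR and both Simon counts exclude treated patients who fail before the cycle 3 scan. For the objective in section 1.1 the estimate is biased upward to the extent that those patients respond less often than those kept.

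The size rests on two assumptions: 15% is the null rate in all treated patients, and the dropped patients are non-responders. Under these, the chance of declaring an inactive drug promising is about 12% at 5% treated loss, 14.5% at 10%, 21% at 20%, and 26% as an upper bound at 25%, against 9.9% by design. With 15% on the evaluable scale the error stays at 9.9%, but the reported ORR still does not describe all treated patients. The consent-based FAS errs in the opposite direction and does not repair this.

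**What to change.** - **Sections 11.4 and 11.5:** make all patients who receive at least one dose (the existing safety population) the primary and response-evaluable population at both stages. Count anyone without a qualifying CR or PR as a non-responder, whatever the reason. Apply 2/9 and 6/23 to this population.
- **Section 11.5:** keep the current per-protocol set as a sensitivity analysis.
- **Section 11.3:** state that 15% and 35% refer to all treated patients; error is then 9.9% and power 80.4%. If 35% was meant for evaluable patients, restate the power on the treated scale (about 58% at 20% loss, 52% at 25%) and decide whether the sample size is still acceptable.

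**Cost.** The population change is a matter of wording and needs no new data collection. The reported ORR will be lower. Stated power may also be lower if 35% was an evaluable-patient figure, and in that case the sample size has to be looked at again.

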## 7. STUDY TESTS AND OBSERVATIONS

Protocol-required tests, observations, and procedures are summarized in the Schedule of Study Assessments. Each cycle consists of 28 days. Patients will self-administer entinostat as described in Section 6.1. During cycle 1, patients will be required to visit the clinic on Days 1, 8, and 15. For all other cycles, patients will be required to visit the clinic on Day 1 and 15 only.

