## **7.2 Day 1 Visit Assessments (All cycles)**

Patients will make clinic visits for tests and observations according to the schedule in Schedule of Study Assessments (Appendix 1). Assessments may be performed up to 2 days and CT/ scans may be performed up to 7 days prior to the scheduled study visit day. The results of study blood tests must be available and reviewed by study site staff for toxicity and adverse events before the next dose of entinostat is administered. Obtaining blood for these tests may be performed locally or drawn by a home health care worker if clinic visits are not practical. Results must be sent to the investigator. Other observations should be performed prior to the next dose of entinostat.

Required procedures are as follows:

- Concomitant medications
- Adverse Events
- Hematology (as at screening)
- Blood chemistries (as at screening with the exception of magnesium which does not need to be done unless clinically indicated)
- Symptom directed PE (capture B symptoms)
- Vital signs and weight
- ECOG performance score
- Clinical disease assessment for palpable or visual lesions
- CT scan for disease assessment (up to 7 days prior to day 1 of odd cycles beginning with Cycle 3). In patients completing >9 cycles, scans are required every 3-4 months and/or omitting the use of contrast dye to every other restaging. Follow-up scans should include

the area of interest, the prospectively selected indicator lesion(s); the same method used at baseline should be used for all serial measurements.

- Entinostat compliance assessment

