#### *Secondary Efficacy*

- Duration of response for patients who achieve CR or PR
- Duration of overall survival
- Duration of progression-free survival

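### As written, the primary PFS and OS estimates leave out patients who died, clinically progressed or stopped drug before the cycle 3 scan, and no all-treated estimate is planned

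*Combined protocol and SAP*

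**What the plan says.** Section 11.2 puts "Duration of overall survival" and "Duration of progression-free survival" under the secondary efficacy heading. Under the primary efficacy heading it lists only the objective response rate.

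Section 11.5 defines three sets.

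- **Per-protocol (evaluable) set.** It "will serve as the population for the primary analysis of the efficacy data in this study". Entry requires at least two completed "cycles of entinostat therapy, irrespective of dose level", and the patient must "Undergo CT scans at Screening and day 1 of cycle 3".
- **Full analysis set (FAS).** This is everyone who has given consent, whether or not they were dosed. Its role is given in one sentence: "The FAS population will serve as the population for a supportive analysis of the primary efficacy analysis".
- **Safety population.** This is everyone who received at least one dose. It is used for safety only.

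On timing, Section 7 states "Each cycle consists of 28 days", and Section 7.2 schedules the "CT scan for disease assessment (up to 7 days prior to day 1 of odd cycles beginning with Cycle 3". Section 6.2 takes patients off treatment once progression or unacceptable toxicity is documented. Nowhere do the documents give a time origin, event definition, censoring rule or estimator for PFS or OS.

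**The concern.** Membership of the per-protocol set is decided by something that happens after treatment starts: being alive, on drug and scanned at about week 8. For a time-to-event endpoint measured from the start of treatment, selecting on a later event produces guarantee-time bias. The early part of the curve is free of events because of who was admitted to it, and everything after is lifted.

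The trial has one arm, so PFS and OS have no internal comparator and will be read as absolute values. An upward shift passes straight into that reading.

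This is separate from the question of the response-rate denominator. Counting early failures as non-responders would correct the response rate. It would not change a PFS or OS curve that admits only patients who reached cycle 3.

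**Working it through.** **Which set applies.** Section 11.5 assigns the efficacy data to the per-protocol set without excepting any endpoint. Section 11.2 classes PFS and OS as efficacy, so they fall under that sentence. The FAS supports the primary efficacy analysis, which under the Section 11.2 headings is response. The all-treated set has no efficacy role.

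**The plan's own figures.** Only response is sized (Section 11.3). With 9 patients in stage 1 and 15% response, the probability of at most one response is 0.85⁹ + 9 × 0.15 × 0.85⁸ = 0.2316 + 0.3679 = 0.5995. The expected sample size is 9 + 14 × (1 − 0.5995) = 14.61. Both match the stated 60% and 14.61. There is no PFS or OS figure to reproduce.

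**Length of the guaranteed period, g.** Two cycles are 2 × 28 = 56 days, which is 8 weeks or 1.84 months. The cycle 3 scan may be 7 days early, giving 56 − 7 = 49 days, or 7 weeks.

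**Assumptions.** The documents give no medians. I assume exponential survival, time from first dose, PFS medians of 16 to 52 weeks and OS medians of 52 to 156 weeks.

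**Formulas, for median m in weeks.**
- All treated: S(t) = 0.5^(t/m).
- Share with an event before g: 1 − S(g).
- Per-protocol curve if those patients are removed: S(t)/S(g) for t > g.
- Setting S(t)/S(g) = 0.5 gives t = m + g, so the median rises by exactly g.

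**Example, m = 24 and g = 8.** S(8) = 0.5^(8/24) = 0.794, so 20.6% have an event before week 8. S(26) = 0.5^(26/24) = 0.472. The per-protocol value is 0.472/0.794 = 0.595.

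| Endpoint, assumed median | Event before week 8 | Read at | All treated | Per-protocol, g = 8 | Per-protocol, g = 7 |
|---|---|---|---|---|---|
| PFS, 16 weeks | 29.3% | week 26 | 32.4% | 45.9% | 43.9% |
| PFS, 24 weeks | 20.6% | week 26 | 47.2% | 59.5% | 57.8% |
| PFS, 36 weeks | 14.3% | week 26 | 60.6% | 70.7% | 69.4% |
| PFS, 52 weeks | 10.1% | week 26 | 70.7% | 78.7% | 77.6% |
| OS, 52 weeks | 10.1% | week 52 | 50.0% | 55.6% | 54.9% |
| OS, 104 weeks | 5.2% | week 52 | 70.7% | 74.6% | 74.1% |
| OS, 156 weeks | 3.5% | week 52 | 79.4% | 82.2% | 81.9% |

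**Why the PFS rows are upper limits.** The formula removes every PFS event before g. No CT is scheduled between screening and cycle 3 day 1, so progression that is visible only on imaging first shows on the cycle 3 scan. A patient who completed two cycles and progressed on that scan stays in the per-protocol set with the event counted. The events removed are mainly early deaths and clinical progressions. Patients who left early for toxicity or by withdrawal are removed too, with any later event.

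**The case against.** **The text does not name PFS or OS.** They are reached through a general term. The FAS sentence could also be read as supporting the primary analysis of all efficacy data, in which case a supportive FAS version of PFS and OS would exist. It is fair that this is an inference. But on that looser reading the primary estimates are still per-protocol, and the FAS can include patients who were never dosed, so it is not an all-treated analysis.

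**The time origin is unstated.** Guarantee time arises only if the clock starts before cycle 3. This stands as a condition. Enrolment or first dose is the ordinary choice, and nothing in the plan points to a later one.

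**A reader might infer that nobody analysed can have an event in the first 8 weeks.** The documents do not support that. The scan window allows about 7 weeks, the plan does not define completing a cycle, and progression on the cycle 3 scan counts for PFS.

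**A reader might take the plan's non-evaluable allowance as the share of early failures and deflate PFS by it.** The ceiling is 25%, and going from 40 enrolled to 32 evaluable implies 1 − 32/40 = 20%. Both are fractions of enrolled patients, and enrolled means consented. They can include people never treated, and dropouts for toxicity or withdrawal need not be events. Neither figure can size the PFS bias.

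**The OS effect is small beside the imprecision.** A shift of 1.84 months is 10%, 8% or 5% of an assumed median of 18, 24 or 36 months. With 32 patients all dead and a 24-month exponential median, the 95% interval is about 24 × exp(±1.96/√32), or 17 to 34 months. Eligibility requires ECOG 0 or 1, so a constant hazard from day 1 may overstate early deaths. This stands, but imprecision does not excuse an avoidable bias.

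**No decision depends on it.** The go/no-go rule uses response only. This also stands and limits the severity.

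**Conclusion.** The point holds. Followed as written, the primary PFS and OS estimates are conditional on reaching the cycle 3 scan, and no analysis of either endpoint in all treated patients is planned. If time runs from enrolment or first dose, both are biased upward.

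The size rests on assumed medians and exponential survival. The median rises by at most about 8 weeks (1.8 months). For OS this is modest: 2.8 to 5.6 percentage points at week 52 for medians of 156 down to 52 weeks. For PFS the gap of 8.0 to 13.5 points at week 26 is an upper limit, because progression first seen on the cycle 3 scan is retained.

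The documents do not support saying that the plan expressly confines PFS and OS to evaluable patients, that the first 8 weeks are wholly free of PFS events, or that OS would be seriously distorted. These are secondary endpoints with no decision threshold, so this should be corrected but does not threaten the primary conclusion.

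**What to change.** In Section 11.5, state the following.

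- PFS and OS are analysed in all patients who received at least one dose, which is the safety population already defined, with time measured from first dose.
- Deaths and progressions before the cycle 3 scan count as events.
- Patients who stop early without an event are censored at their last disease assessment for PFS and at last contact for OS. This rule is needed because scheduled long-term contact after treatment ends is by telephone.
- Any per-protocol curve is a sensitivity analysis only, labelled as conditional on reaching cycle 3.

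Restarting the PFS clock at week 8 is not a good substitute. Progression on a scan at, or up to 7 days before, cycle 3 day 1 would fall at or before time zero.

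The cost is a few sentences. No new data are needed, because Section 7.6 and the contact footnote in Appendix 1 already provide follow-up for progression and survival. The estimates become somewhat less favourable, and censoring patients who stop for toxicity at their last assessment may itself be informative, so their number should be reported.
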